4.15.2 Laboratory Data

QMD Ref: CCI	Governing QMD: CCI
Confidentiality Statement	
CCI	

CCI		Sponsor: Theseus Pharmaceuticals, Inc.	
CCI		Protocol Number: THE630-21-101	
STATISTICAL ANALYSIS PLAN. PHASE 2-3-4			

Laboratory samples will be analyzed by local laboratories. For reporting purposes, lab parameters will be reported using SI units.

Each measurement (continuous data) will be classed as below, within, or above normal range, based on ranges supplied by the laboratory used. To identify laboratory values of potential clinical importance, National Cancer Institute Common Terminology Criteria for Adverse Events (CTCAE) will be used to assign grades for select laboratory parameters where applicable (See [Appendix 4](#)). A shift table representing two-way frequency tabulation for baseline and the worst post-baseline value according to the CTCAE grade, by cohort and overall, will be provided. For analysis purpose, patients with a lab parameter value that does not meet CTCAE criteria (e.g., value is within normal range) at baseline or any time post-baseline, will be assigned a Grade of 0 for said visit.

The incidence of patients meeting Hy’s law criteria will be summarized for any time, post-baseline (See [Appendix 5](#)).

A listing of any abnormal laboratory measurements recorded throughout the study will be presented.

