STATISTICAL ANALYSIS PLAN. PHASE 2-3-4			

Table Number	Table Title	Validation Method	Shell Number (if repeat)
14.3.2.4 DE	TEAEs Reported as Dose Limiting Toxicity, Listing – Full Analysis Set <Phase>	IP	
14.3.3	Narratives of Deaths, Other Serious and Certain Other Significant Adverse Events		
14.3.4	Abnormal Laboratory Values		
14.3.4.1 DE	Laboratory, Listing of Abnormal Values – Full Analysis Set <Phase>	IP	
14.3.4.2 DE	Hematology, CTCAE Grade Shifts from Baseline to Worst Post-Baseline Grade – Full Analysis Set <Phase>	IP	
14.3.4.3 DE	Chemistry, CTCAE Grade Shifts from Baseline to Worst Post-Baseline Grade – Full Analysis Set <Phase>	IP	14.3.4.2
14.3.4.4 DE	Coagulation, CTCAE Grade Shifts from Baseline to Worst Post-Baseline Grade – Full Analysis Set <Phase>	IP	14.3.4.2
14.3.4.5 DE	Potential Hepatotoxicity based on Hy’s law – Full Analysis Set <Phase>	IP	
14.3.4.6 DE	Laboratory, Listing of Patients with Potential Hepatotoxicity based on Hy’s law -Full Analysis Set <Phase>	IP	
14.3.5	Extent of Exposure, Dosage Information, And Compliance		
14.3.5.1 DE	Exposure to Study Drug- Full Analysis Set <Phase>	IP	
14.3.5.2 DE	Compliance to Study Drug During Cycle 1 -Full Analysis Set <Phase>	IP	
14.3.6	Vital Signs and Physical Examination		
14.3.6.1 DE	Vital Signs: Blood Pressure Shifts from Baseline to Maximum Post-baseline Value – Full Analysis Set <Phase>	IP	
14.3.7	Other Safety		
14.3.7.1 DE	Echocardiogram/MUGA, Descriptive Statistics-Full Analysis Set <Phase>	IP	
14.3.7.2 DE	ECG, QTcF values of Potential Clinical Concern Any Time, Post-baseline by Category-Full Analysis Set <Phase>	IP	
14.3.8	Concomitant Medication		
14.4	PK Tables		
QMD Ref: CCI		Governing QMD: CCI	
Confidentiality Statement			
CCI			

CCI		Sponsor: Theseus Pharmaceuticals, Inc.	
CCI		Protocol Number: THE630-21-101	
STATISTICAL ANALYSIS PLAN. PHASE 2-3-4			

Table Number	Table Title	Validation Method	Shell Number (if repeat)
14.5	PD Tables		
14.6	Other Data		

QMD Ref: CCI	Governing QMD: CCI
Confidentiality Statement	
CCI	

CCI			
CCI		Sponsor:	Theseus Pharmaceuticals, Inc.
		Protocol Number:	THE630-21-101
STATISTICAL ANALYSIS PLAN. PHASE 2-3-4			

Figure Number	Figure Title	Validation Method	Shell Number (if repeat)
14.2.1.3 DE	Best % Change from Baseline in Sum of the Longest Diameter of Target Lesion -Full Analysis Set <Phase>	IP	
14.2.1.4 DE	Swimmers Plot, Duration of treatment -Full Analysis Set <Phase>	IP	

QMD Ref: CCI	Governing QMD: CCI
Confidentiality Statement	
CCI	

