Sodium	Hypernatremia	Increase	>ULN-150 mmol/L	>150-155 mmol/L	>155-160 mmol/L	>160 mmol/L

QMD Ref: CCI	Governing QMD: CCI
Confidentiality Statement	
CCI	

CCI		Sponsor: Theseus Pharmaceuticals, Inc.	
CCI		Protocol Number: THE630-21-101	
STATISTICAL ANALYSIS PLAN. PHASE 2-3-4			

Parameter	CTCAE Term	Directionality	Grade 1	Grade 2	Grade 3	Grade 4
Potassium	Hypokalemia	Decrease	<LLN-3.0 mmol/L	N/A (for purpose of this study)	<3.0-2.5 mmol/L	<2.5 mmol/L
Magnesium	Hypomagnesemia	Decrease	<LLN-1.2 mg/dL; <LLN-0.5 mmol/L	<1.2-0.9 mg/dL; <0.5-0.4 mmol/L	<0.9-0.7 mg/dL; <0.4-0.3 mmol/L	<0.7 mg/dL; <0.3 mmol/L
Magnesium	Hypermagnesemia	Increase	>ULN-3.0 mg/dL; >ULN-1.23 mmol/L	>3.0-8.0 mg/dL; >1.23-3.30 mmol/L	>8.0 mg/dL; >3.30 mmol/L	N/A
Phosphorous (based on CTCAE v4.03 criteria)	Hypophosphatemia	Decrease	<LLN - 2.5 mg/dL; <LLN - 0.8 mmol/L	<2.5 - 2.0 mg/dL; <0.8 - 0.6 mmol/L	<2.0 - 1.0 mg/dL; <0.6 - 0.3 mmol/L	<1.0 mg/dL; <0.3 mmol/L
Calcium (Total) (correct calcium numeric criteria will be applied)	Hypocalcemia	Decrease	Corrected serum calcium of <LLN-8.0 mg/dL; <LLN-2.0 mmol/L	Corrected serum calcium of <8.0-7.0 mg/dL; <2.0-1.75 mmol/L	Corrected serum calcium of <7.0-6.0 mg/dL; <1.75-1.5 mmol/L	Corrected serum calcium of <6.0 mg/dL; <1.5 mmol/L

QMD Ref: CCI	Governing QMD: CCI
Confidentiality Statement	
CCI	

CCI		Sponsor: Theseus Pharmaceuticals, Inc.	
CCI		Protocol Number: THE630-21-101	
STATISTICAL ANALYSIS PLAN. PHASE 2-3-4			

Parameter	CTCAE Term	Directionality	Grade 1	Grade 2	Grade 3	Grade 4
Calcium Total (correct calcium numeric criteria will be applied)	Hypercalcemia	Increase	Corrected serum calcium of >ULN-11.5 mg/dL; >ULN-2.9 mmol/L	Corrected serum calcium of >11.5-12.5 mg/dL; >2.9-3.1 mmol/L	Corrected serum calcium of >12.5-13.5 mg/dL; >3.1-3.4 mmol/L	Corrected serum calcium of >13.5 mg/dL; >3.4 mmol/L
ALT	Alanine Aminotransferase Increased	Increase	>ULN-3.0 x ULN if baseline was normal; 1.5-3.0 x baseline if baseline was high abnormal (> ULN)	>3.0-5.0 x ULN if baseline was normal; >3.0-5.0 x baseline if baseline was high abnormal (> ULN)	>5.0-20.0 x ULN if baseline was normal; >5.0-20.0 x baseline if baseline was high abnormal (> ULN)	>20.0 x ULN if baseline was normal; >20.0 x baseline if baseline was high abnormal (> ULN)

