AST	Aspartate Aminotransferase Increased	Increase	>ULN-3.0xULN if baseline was normal; 1.5-3.0x baseline if baseline was high abnormal (i.e., > ULN)	>3.0-5.0xULN if baseline was normal; >3.0-5.0x baseline if baseline was high abnormal (i.e., > ULN)	>5.0-20.0xULN if baseline was normal; >5.0-20.0x baseline if baseline was high abnormal (i.e., > ULN)	>20.0xULN if baseline was normal; >20.0x baseline if baseline was abnormal high abnormal (i.e., > ULN)
Total bilirubin	Blood Bilirubin Increased	Increase	>ULN-1.5 x ULN if baseline was normal; > 1.0-1.5 x baseline if baseline was high abnormal (i.e., > ULN)	>1.5-3.0 x ULN if baseline was normal; >1.5-3.0 x baseline if baseline was high abnormal (i.e., > ULN)	>3.0-10.0 x ULN if baseline was normal; >3.0-10.0 x baseline if baseline was high abnormal (i.e., > ULN)	>10.0 x ULN if baseline was normal; >10.0 x baseline if baseline was high abnormal (i.e., > ULN)
Albumin	Hypoalbuminemia	Decrease	<LLN-3 g/dL; <LLN-30 g/L	<3-2 g/dL; <30-20 g/L	<2 g/dL; <20 g/L	
Creatinine	Creatinine Increased	Increase	>ULN-1.5 x ULN	>1.5-3.0 x baseline; >1.5-3.0 x ULN	>3.0 x baseline; >3.0-6.0 x ULN	>6.0 x ULN

QMD Ref: CCI	Governing QMD: CCI
Confidentiality Statement	
CCI	

CCI		
CCI	Sponsor:	Theseus Pharmaceuticals, Inc.
	Protocol Number:	THE630-21-101
STATISTICAL ANALYSIS PLAN. PHASE 2-3-4		

Parameter	CTCAE Term	Directionality	Grade 1	Grade 2	Grade 3	Grade 4
Amylase (based on CTCAE v4.03 criteria)	Serum Amylase Increased	Increase	>ULN-1.5 x ULN	>1.5-2.0 x ULN;	>2.0-5.0 x ULN	>5.0 x ULN
Lipase (based on CTCAE v4.03 criteria)	Lipase Increased	Increase	>ULN-1.5 x ULN	>1.5-2.0 x ULN	>2.0-5.0 x ULN	>5.0 x ULN
CK (Creatinine Kinase)	CPK Increased	Increase	>ULN-2.5 x ULN	>2.5 x ULN-5 x ULN	>5 x ULN-10 x ULN	>10 x ULN
Alkaline phosphatase	Alkaline Phosphatase increased	Increase	>ULN-2.5xULN if baseline was normal; 2.0-2.5x baseline if baseline was high abnormal (i.e., > ULN)	>2.5-5.0xULN if baseline was normal; >2.5-5.0x baseline if baseline was high abnormal (i.e., > ULN)	>5.0-20.0xULN if baseline was normal; >5.0-20.0x baseline if baseline was high abnormal (i.e., > ULN)	>20.0xULN if baseline was normal; >20.0x baseline if baseline was high abnormal (i.e., > ULN)

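### The chemistry shift table puts every patient at baseline Grade 0 for ALT, AST, ALP and total bilirubin, so its baseline axis says nothing for these four tests

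*SAP*

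**What the plan says.** SAP 4.15.2 (Laboratory Data) provides, by cohort and overall, "A shift table representing two-way frequency tabulation for baseline and the worst post-baseline value according to the CTCAE grade". For chemistry this is Table 14.3.4.3 DE in SAP Section 9, titled "Chemistry, CTCAE Grade Shifts from Baseline to Worst Post-Baseline Grade".

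The same section sets a default: "patients with a lab parameter value that does not meet CTCAE criteria (e.g., value is within normal range) at baseline or any time post-baseline" are given Grade 0 for that visit.

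Appendix 4 (section 12.1) holds one set of numeric criteria, with no separate rule for the baseline visit. For four tests the criteria depend on the patient's baseline. If it was normal, grades follow multiples of ULN. If it was above ULN, grades follow multiples of the patient's own baseline, and Grade 1 is:

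- ALT: "1.5-3.0 x baseline if baseline was high abnormal (> ULN"; AST has the same limits
- ALP: "2.0-2.5x baseline if baseline was high abnormal (i.e., > ULN"
- Total bilirubin: "> 1.0-1.5 x baseline if baseline was high abnormal (i.e., > ULN"

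The Hy's law summary uses fixed ULN bands (Appendix 5), but covers post-baseline values only: "criteria will be summarized for any time, post-baseline".

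**The concern.** A shift table needs a scale that can place the baseline value as well as the later one. Baseline-relative criteria grade change from baseline. They cannot grade the baseline itself, because its ratio to itself is always 1.0. With the Grade 0 default, a patient who enters with ALT above 3 and up to 5 x ULN (allowed if due to the malignancy) sits in the same row as a patient with normal values. A reader will take that row to mean normal, since the SAP's own example of Grade 0 is a value within the normal range.

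This is the only listed table that sets baseline against post-baseline values for these tests. If its baseline axis is empty, no table separates patients who entered with abnormal liver tests from those who entered normal, in a study whose Phase 1 primary endpoint is the safety profile.

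**Working it through.** **Inputs**

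- Baseline is a single value per patient, the last before first dose (SAP 4.2.2).
- Grade criteria: SAP Appendix 4. Grade 0 default: SAP 4.15.2.
- Entry limits (Protocol 4.1, criterion 7): ALT and AST up to 3 x ULN, or 5 x ULN if due to malignancy; bilirubin up to 1.5 x ULN, or below 3.0 x ULN with Gilbert syndrome. There is no ALP limit. Abnormal baselines are therefore possible for all four tests.

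**Step 1: the grade of the baseline value.** Let b be the baseline in multiples of ULN.

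- If b is at or below 1, the value is not above ULN, so it is Grade 0.
- If b is above 1, the ratio is b/b = 1.0. This is below the Grade 1 floor of 1.5 (ALT, AST) and 2.0 (ALP), and it is not strictly above 1.0 (bilirubin). It meets no criterion, so it is Grade 0.

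Grading each b from 0.01 to 25 in steps of 0.01 by these rules gives Grade 0 only, for all four tests. On the ULN multiples the same values spread over Grades 0 to 4. Creatinine, whose criteria include ULN multiples whatever the baseline, also spreads over Grades 0 to 4. The semicolon that Appendix 4 reads as *or* does not help, because the two clauses apply to mutually exclusive baselines.

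**Step 2: what the table would show.** Ratio = post-baseline value / baseline.

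| Test | Baseline (x ULN) | Post-baseline (x ULN) | Ratio | Shown | On ULN multiples |
|---|---|---|---|---|---|
| ALT | 0.9 | 5.5 | not used | 0 to 3 | 0 to 3 |
| ALT | 4.0 | 5.5 | 1.375 | 0 to 0 | 2 to 3 |
| ALT | 4.9 | 7.3 | 1.49 | 0 to 0 | 2 to 3 |
| ALT | 2.5 | 7.4 | 2.96 | 0 to 1 | 1 to 3 |
| ALP | 3.0 | 5.9 | 1.97 | 0 to 0 | 2 to 3 |
| Bilirubin | 1.5 | 3.1 | 2.07 | 0 to 2 | 1 to 3 |

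The first two rows have the same post-baseline value and the same baseline row, but appear as Grade 3 and Grade 0.

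**Step 3: when 0 to 0 hides a rise in ULN grade.** This needs the Grade 1 floor times b to exceed the next ULN cut-point.

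- ALT/AST, next cut-point 3 x ULN: 1.5b > 3, so b above 2.0 and up to 3.0.
- ALT/AST, next cut-point 5 x ULN: 1.5b > 5, so b above 3.33 and up to the 5.0 entry limit.
- ALP, next cut-point 2.5 x ULN: 2.0b > 2.5, so b above 1.25 and up to 2.5. For b above 2.5 and up to 5.0, 2.0b always exceeds the next cut-point of 5.
- Bilirubin: any rise from an abnormal baseline has a ratio above 1.0 and is at least Grade 1, so 0 to 0 does not arise. Only the baseline axis collapses.

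**Step 4: larger ALT rises.** Grade 3 starts above 5 x baseline. From b = 2.0 that is above 10.0 x ULN, and from b = 3.0 above 15.0 x ULN. Post-baseline values of 5.01 to 10.0 and 5.01 to 15.0 x ULN respectively are therefore shown below Grade 3, although they exceed the 5 x ULN cut-point used for a normal baseline.

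**The case against.** The strongest reply is that baseline-relative grading is deliberate. Appendix 4 adopts CTCAE v5.0, as the protocol does, and under those criteria a move from 4.0 to 5.5 x ULN is meant to grade lower than a move from 0.9 to 5.5. Calling the post-baseline grades too low is then a preference for another scale. That stands for the post-baseline axis, and Step 4 describes a consequence of the convention rather than a mistake in it. It does not rescue the baseline axis.

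Second, the data are not lost. The abnormal-value listing (14.3.4.1 DE) remains, with 32 patients it can be read by eye, and the Hy's law table places ALT and AST on fixed ULN bands; 5.5 and 7.3 x ULN both fall in its 5 to below 8 band. This also stands, and it limits the loss to the tabulation.

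Third, DLTs come from adverse events, not from this table; enrollment has stopped; the number of affected patients is unknown; and the ALT examples at 4.0 and 4.9 x ULN need the malignancy exception. All true. The 2.5 x ULN example, however, lies within the general entry limit.

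Fourth, the table shells are not in the documents, and programmers might grade baseline on ULN multiples. The SAP does not say so. If that is the intent, it has to be written down.

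**Conclusion.** The point holds. With Appendix 4 and the Grade 0 default applied as written, every patient with a baseline value is Grade 0 at baseline for ALT, AST, ALP and total bilirubin, and the two-way table carries one-way information for these tests. The other chemistry tests are graded on absolute limits or on limits of normal (creatinine also on baseline multiples) and are not affected.

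The collapse of the baseline axis is certain from the text and does not depend on the data. How many patients are misplaced depends on how many of the 32 had abnormal baselines, which the documents do not report. The worked values are illustrations, chosen within the entry limits; the ALP baseline is assumed, since the protocol sets no ALP limit. The consequence is a safety table that can be misread, not a change to DLTs or to any efficacy result. It should be corrected.

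**What to change.** For ALT, AST, ALP and total bilirubin, build Table 14.3.4.3 DE on the ULN-multiple cut-points that Appendix 4 already gives for a normal baseline, and use them on both axes. Report the CTCAE v5.0 baseline-relative worst post-baseline grade in a separate, labelled one-way row, so that the v5.0 grading is kept. State in SAP 4.15.2 and Appendix 4 which scale each part uses.

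The cost is a small programming change to one table, with no new data. The downside is that stable tumour-related elevations will show as Grade 1 or 2 at both time points (possibly higher for ALP, which has no entry limit). For a shift table that is the correct picture.

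A lesser alternative is to split the baseline row into within and above normal range, using the classification already in 4.15.2. It restores the normal/abnormal distinction, but still puts a baseline of 1.2 x ULN beside one of 4.9 x ULN.

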### 6.3.11 End of Treatment

The End of Treatment visit must be performed within 14 days ( $\pm 7$  days) of the patient's last dose of study drug or the patient/Investigator decision to discontinue study treatment, whichever occurs later.

The following evaluations and procedures will be performed during this visit:

- Vital signs
- ECOG performance status test
- The following procedures must be performed if they were conducted more than 14 days prior to the End of Treatment visit or, if in the opinion of the Investigator, there is reason to believe the results have substantially changed:
  - Physical examination
  - Laboratory assessments: hematology, chemistry (including Troponin T), coagulation, and urinalysis
  - Pregnancy test for FOCP
  - 12-lead ECG (single)
  - Echocardiogram/MUGA scan
- Disease assessment by CT scan and MRI (if more than 4 weeks have passed since the last imaging assessment and progression had not previously been documented)
- THE-630 compliance
- Adverse events assessment
- Recording of concomitant medications
- Blood sample for exploratory biomarkers (at disease progression, only)

- Tissue sample for exploratory biomarker analysis (optional; at disease progression, only)

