#### **8.2.5 Clinical Laboratory Evaluations**

A change in a clinical laboratory value can represent an AE if the change is clinically relevant or if, during treatment with the study drug, a shift of a parameter is observed from a normal value to an abnormal value, or a further worsening of an already abnormal value. When evaluating such changes, the extent of deviation from the reference range, the duration until return to the reference range, either while continuing treatment or after the end of treatment with the study drug, and the range of variation of the respective parameter within its reference range, must be taken into consideration.

If, at the end of the treatment phase, there are abnormal clinical laboratory values which were not present at baseline, further clinical or laboratory investigations should be performed until the values return to within the reference range or until a plausible explanation (e.g., concomitant disease) is found for the abnormal clinical laboratory values.

The Investigator should decide, based on the above criteria and the clinical condition of a patient, whether a change in a clinical laboratory parameter is clinically significant and therefore represents an AE.

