### 9.6.2 QTcF Analysis

Descriptive statistics of maximum QTcF and change from baseline will be calculated following the ICH-E14 guidelines: the proportion of treated patients with at least 1 on-drug QTcF value >450 ms, 480 ms, and 500 ms; and the proportion of treated patients with a maximum change in QTcF from baseline >30 ms and >60 ms. The Fridericia correction (QTcF) will be used throughout. The association between QTcF changes and plasma levels of THE-630 will be analyzed using mixed effects models.

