4.2.13.2 Dose Limiting Toxicities (DLT)

DLTs during Phase 1 (dose escalation phase) are defined as any treatment-emergent adverse event (AE) that meets the following criteria within the first 28 days of treatment (e.g, occurring during Cycle 1) and for which the relationship to THE-630 cannot be ruled out:

- Non-hematologic toxicities
 - Any ≥ Grade 3 non-hematologic toxicity, with the exception of:

QMD Ref: CCI		Governing QMD: CCI	
Confidentiality Statement			
CCI			

CCI			
CCI	Sponsor:		Theseus Pharmaceuticals, Inc.
	Protocol Number:		THE630-21-101
STATISTICAL ANALYSIS PLAN. PHASE 2-3-4			

- Self-limiting or medically controllable toxicities (e.g., nausea, fatigue, electrolyte disturbances) lasting ≤ 3 days
 - Grade 3 vomiting or diarrhea lasting ≤ 3 days
 - Grade 3 elevations of creatine kinase (CK) that are asymptomatic, i.e., not accompanied by muscle pain or worsening renal function or other signs of rhabdomyolysis or cardiac muscle damage (such as abnormal CK-MB, Troponin) and recovered to \leq Grade 1 or baseline in <72 hours
 - Grade 3 hypertension that recovers to Grade 2 or below within 5 days
 - Alopecia
- Hematologic toxicities
 - Febrile neutropenia (fever, $>101^{\circ}\text{F}$ [$>38.3^{\circ}\text{C}$]; ANC $<0.5 \times 109/\text{L}$)
 - Prolonged Grade 4 neutropenia (≥ 7 days)
 - Neutropenic infection: \geq Grade 3 neutropenia with \geq Grade 3 infection
 - Thrombocytopenia \geq Grade 3 with bleeding or Grade 4 without bleeding lasting ≥ 7 days
 - Missed $\geq 25\%$ of planned doses of THE-630 (in the aggregate, not necessarily consecutive) over 28 days due to AEs for which the relationship to THE-630 cannot be ruled out in the first cycle [note the treatment-related AE(s) included should not have met other DLT criteria]

DLTs will be reported as AEs and identified as a DLT in the database.

4.2.13.3 *Unscheduled Visits*

Only scheduled post-baseline laboratory, vital signs, ECHO/MUGA and ECG values will be tabulated by visit. Certain summaries may have any time, post-baseline/worst post-baseline/minimum post-baseline/maximum post-baseline which would include post-baseline scheduled/repeat/ unscheduled assessments. All post-baseline assessments will be listed in the relevant appendices to the CSR.

4.2.14 **Efficacy endpoints**

QMD Ref: CCI	Governing QMD: CCI
Confidentiality Statement	
CCI	

CCI		Sponsor: Theseus Pharmaceuticals, Inc.	
CCI		Protocol Number: THE630-21-101	
STATISTICAL ANALYSIS PLAN. PHASE 2-3-4			

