4.15.3 Vital Signs

To identify vital signs values of potential clinical importance, the following criteria will be used for the following vital signs parameters: systolic blood pressure (SBP) and diastolic blood pressure (DBP).

Parameter	Category (levels)
SBP (mmHg)	<120 mmHg 120-139 mmHg 140-159 mmHg ≥ 160 mmHg
DBP (mmHg)	<80 mmHg 80-89 mmHg 90-99 mmHg ≥ 100 mmHg

For systolic and diastolic blood pressure, a shift table representing two-way frequency tabulation for baseline and the maximum post-baseline value according to the above criteria, by cohort and overall, will be provided along with summary of any increases in category level.

QMD Ref: CCI	Governing QMD: CCI
Confidentiality Statement	
CCI	

CCI			
CCI	Sponsor:		Theseus Pharmaceuticals, Inc.
	Protocol Number:		THE630-21-101
STATISTICAL ANALYSIS PLAN. PHASE 2-3-4			

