4.15.6 Electrocardiogram Data

The number (%) of patients meeting the following criteria at any time, post-baseline will be summarized by cohort and overall:

- QT interval (ms)
 - >500 & baseline \leq 500
- QTcF maximum increase (on treatment defined as any assessment on or after first dose up to last dose + 30 days)
 - No increase
 - >0 to <30 ms
 - 30 to 60 ms
 - >60 ms
- QTcF (ms)
 - >500 & baseline \leq 500
 - >480 & baseline \leq 480
 - >450 & baseline \leq 450
- Heart Rate (bpm)
 - <60 bpm
 - <50 bpm
 - >100 bpm
 - >100 bpm and 25% increase from baseline
 - < 50 bpm and 25% decrease from baseline

QMD Ref: CCI	Governing QMD: CCI
Confidentiality Statement	
CCI	

CCI			
CCI		Sponsor:	Theseus Pharmaceuticals, Inc.
		Protocol Number:	THE630-21-101
STATISTICAL ANALYSIS PLAN. PHASE 2-3-4			

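### SAP 4.15.6 counts ECG thresholds with no end date, although its QTcF-increase row stops at last dose + 30 days and the protocol asks for on-drug values; laboratory and blood pressure extremes are open-ended too

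*SAP*

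**What the plan says.** **Open-ended summaries in the SAP.**

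- Laboratory grades (4.15.2; Tables 14.3.4.2 to 14.3.4.4): "A shift table representing two-way frequency tabulation for baseline and the worst post-baseline value according to the CTCAE grade". The Hy's law incidence in the same section (Table 14.3.4.5) is also taken over all post-baseline time.
- Blood pressure (4.15.3; Table 14.3.6.1): "a shift table representing two-way frequency tabulation for baseline and the maximum post-baseline value according to the above criteria".
- ECG (4.15.6): "The number (%) of patients meeting the following criteria at any time, post-baseline will be summarized by cohort and overall". This heads the QT, QTcF >450/480/500 ms and heart-rate rows. Table 14.3.7.2 is the only ECG table in SAP section 9. Its title names QTcF only, so placing the QT and heart-rate rows there is an inference.

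SAP 4.2.13.3 describes worst, maximum and any-time summaries as ones "which would include post-baseline scheduled/repeat/ unscheduled assessments". SAP 4.2.2 fixes where post-baseline begins, and nothing general fixes where it ends.

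**Where the SAP does set an end.** One row of 4.15.6 reads "QTcF maximum increase (on treatment defined as any assessment on or after first dose up to last dose + 30 days". SAP 4.15.1 applies the same 30 days to adverse events with new onset.

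**The protocol.** Section 9.6.2 defines the QTcF threshold analysis as "the proportion of treated patients with at least 1 on-drug QTcF value" above each cut-off, and the synopsis agrees. SAP section 7 presents the analyses as broadly in line with the protocol apart from reduced scope. It does not mention a change of window.

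**The concern.** Two things look wrong, and they differ in weight.

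The first is an inconsistency inside one small section. The QTcF increase rows and the QTcF threshold rows describe the same ECGs but take them from different periods. A reader of Table 14.3.7.2 would expect the rows to agree. The threshold rows also depart from the protocol's on-drug analysis, and this is not declared.

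The second is that the laboratory, Hy's law and blood pressure extremes have no end either. A value taken long after dosing stopped would be tabulated under the patient's THE-630 dose level, next to adverse event tables that mostly stop at 30 days. The safety profile is the Phase 1 primary endpoint (SAP 3.1.1), so its tables should rest on one stated period.

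**Working it through.** No power or precision figure is involved. The check compares the windows and then asks how a late value could arise.

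**1. Windows side by side**

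| Summary | Start | End |
|---|---|---|
| New-onset TEAEs (SAP 4.15.1) | first dose | last dose + 30 days |
| QTcF maximum increase (SAP 4.15.6) | first dose | last dose + 30 days |
| QT, QTcF and heart-rate thresholds (SAP 4.15.6) | after baseline | none |
| QTcF thresholds (Protocol 9.6.2) | on drug | on drug, not further defined |
| Worst laboratory grade, Hy's law (SAP 4.15.2) | after baseline | none |
| Maximum blood pressure (SAP 4.15.3) | after baseline | none |

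**2. When the End of Treatment visit can fall**

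Protocol 6.3.11 allows 14 days (± 7), counted from the "last dose of study drug or the patient/Investigator decision to discontinue study treatment, whichever occurs later". Let *g* be the days from last dose to the decision to stop. Then:

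- nominal visit day after last dose = *g* + 14
- latest visit day after last dose = *g* + 14 + 7 = *g* + 21

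| *g* | Nominal | Latest |
|---|---|---|
| 0 | 14 | 21 |
| 14 (a two-week hold) | 28 | 35 |
| 28 (the surgical interruption in Protocol 5.7.2) | 42 | 49 |

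The visit passes day 30 when *g* + 14 > 30, so *g* ≥ 17 for a nominal visit, or when *g* + 21 > 30, so *g* ≥ 10 for the latest visit. Without a prior hold it cannot pass day 30. Laboratory tests and the ECG may be omitted if done in the previous 14 days; vital signs are always taken.

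**3. Other routes**

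- Unscheduled or repeat assessments, which 4.2.13.3 admits.
- Laboratory values under Protocol 8.2.5: "further clinical or laboratory investigations should be performed until the values return to within the reference range", or until plausibly explained. This has no time limit, but it covers only abnormalities present at the end of treatment and not at baseline. It changes a worst grade only if the value worsens further. It gives no route for blood pressure or ECG.
- The 30-day contact (Protocol 6.4.1) and survival follow-up (6.4.2) include no laboratory test, vital sign or ECG.

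**4. What the mixed ECG windows allow (illustration)**

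Take a QTcF of 505 ms on day 40 after last dose, reachable as 28 + 12 with 12 inside the 7-to-21-day range. Assume a baseline no higher than the 470 ms screening limit (exclusion criterion 6). The rise is at least 505 − 470 = 35 ms. The patient enters the >500 ms row, but this ECG is ignored in the increase rows, where it would otherwise count in at least the 30 to 60 ms category. If no earlier on-treatment ECG had risen, the patient would be shown as having no increase.

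**5. Weight of one such patient**

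1/32 = 3.1 percentage points overall (32 enrolled, SAP section 1); 1/6 = 16.7 points in a cohort of 6; 1/3 = 33.3 points in a cohort of 3. These figures show how coarse the tables are. They do not estimate an effect.

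**The case against.** The any-time wording is deliberate. It recurs in 4.2.13.3, 4.15.2, 4.15.6 and the title of Table 14.3.7.2. It is also conservative, because it cannot hide a late signal. The counts are descriptive and assign no causality. DLTs and the MTD rest on Cycle 1, which late values cannot reach. Enrollment has stopped and Phase 2 will not open. The routes to a late value are narrow: day 35 and day 49 each need a hold followed by a visit at the very end of its allowance.

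Most of this stands and lowers the severity. It does not explain why one row of 4.15.6 has a limit and its neighbors do not, or why the departure from on-drug values is undeclared.

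A reader might go further and infer that results obtained more than 30 days after dosing, or on the next anticancer drug, are in fact being reported as THE-630 toxicity. The documents do not support that. No laboratory test, vital sign or ECG is scheduled after End of Treatment, and no visit is tied to the start of another drug. Such a value is possible: Protocol 5.8.1 lists new therapy as a reason to discontinue and still asks for End of Treatment assessments. Nothing shows that one exists.

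**Conclusion.** The point holds as a minor inconsistency. On the text alone, the threshold rows of SAP 4.15.6 use a different window from the QTcF increase row and a wider one than Protocol 9.6.2, and SAP section 7 does not disclose it. The worst laboratory grade, Hy's law and maximum blood pressure summaries share the missing end date.

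The practical size is unknown and probably small. It depends on how many patients had a hold of at least 10 days before the decision to stop, an unscheduled late assessment, or a laboratory value that worsened during off-drug follow-up. The documents give none of these numbers. The visit-day arithmetic assumes that the stated visit allowance was kept. Conclusions about DLTs and the MTD are unaffected.

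**What to change.** 1. Apply the window already in SAP 4.15.6, first dose to last dose + 30 days, to every row of Table 14.3.7.2. For consistency, apply it also to Tables 14.3.4.2 to 14.3.4.5 and 14.3.6.1.
2. End the window earlier at the start of new systemic anticancer therapy where that date is recorded. The protocol says new therapies should be reported (6.4.2) but specifies start and stop dates only for prior therapy (7.1.3).
3. State in SAP section 7 how this window implements the protocol's on-drug wording. The protocol does not define the term, and 30 days after the last dose is not literally on drug.
4. Keep late values visible. Laboratory values stay in listing 14.3.4.1, and Hy's law listing 14.3.4.6 should flag any outside the window so that it agrees with Table 14.3.4.5. Late ECG and blood pressure values need a footnote or short listing: 4.2.13.3 says post-baseline assessments will be listed, but SAP section 9 contains no listing for either.

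The cost is a sentence or two in the SAP, one date filter and one footnote or listing. The downside is small: a true drug effect first seen after the window would move from the summary table to the footnote or listing.
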